In Study 3, we propose to test the refined interventions with a larger group of combat wounded veterans ($N = 60$ combat wounded veterans; 30 MMMI; 30 ES group). After completing the baseline measures, participants will be randomly assigned to program. We will collect information on acceptability, adherence, and implementation/practicality in the two intervention arms, as well as primary moral injury symptoms (e.g., guilt, shame), possible mechanisms of changes (e.g., acceptance, nonjudgment, compassion), and possible secondary outcomes (e.g., mental health symptoms, substance use), which will help inform key variables to include in a large-scale sufficiently powered RCT. See Table 3.

Sample Size Determination

Prior to determining the sample size for Study 3, we examined the literature on determination of sample size for feasibility studies.¹⁵⁵⁻¹⁵⁷ We specifically examined prior eligibility, refusal, randomization and session and data completion rates. We also considered practical aspects such as eligibility criteria, refusal and dropout rates,

expected interview and data completion rates, therapist hours and length of training, supervision, fidelity coding, and timeline. Overall, the majority of feasibility studies had modest sample sizes with varying rates of participation completion: 57% (n = 21),¹⁰⁷ 81% (n = 33),⁹⁷ and 77% (n = 37).¹¹⁰ Based on averages from previous studies,^{97,107,110} we will recruit 60 combat wounded veterans. Furthermore, we expect an ineligible rate/refusal rate of 30% (n = 18) and that an additional 18.8% (n = 8) will attend no sessions and/or not complete the post-training semi-structured interview or other survey measures, for a conservative completion rate of 34 participants. Given that the MMMI and ES support group will be equal in delivery, facilitation, group size, length, home practice burden, we do not anticipate different group completion rates.

Aim 2: Examine the Intervention's Feasibility, Acceptability, and Preliminary Efficacy (Study 2)

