In Study 2, we propose to test our ability to recruit and retain participants, to implement the designed protocol, and to determine treatment adherence of the refined MMMI intervention as compared to a facilitator-led ES comparison group (N = 20 combat wounded veterans; 10 MMMI; 10 ES). The two groups (MMMI and ES) will not differ in the delivery (i.e., live facilitator led interactive web-based, number of sessions, length of sessions, and have manualized treatments). Further, some content will be identical (e.g., introductions, icebreakers) or similar (e.g., benchmarks, semi-structured interview). We will gather audiotaped semi-structured interviews and brief benchmark measures to assess the feasibility, acceptability, participant comments and suggestions, as well as and participant acceptance, satisfaction, and compliance data. See Table 1.

Because there is treatment-as-usual comparable to MMMI, treatment-as-usual comparable to MMMI, several factors guided our decisions in developing the control group. In a different patient population, co-I [name] developed and compared an ES group to a mindfulness training group. Although the mindfulness group developed specific mindfulness skills, the two groups did not differ in their ratings of the credibility of their assigned interventions.¹⁴² Also, an active control condition provides a stronger study design.¹⁵¹ Third, treatment of the control condition should only differ from the experimental condition in the 'non-receipt' of the 'active ingredient'.¹⁵² Also, 59% of veterans who took part in a Wounded Warrior Project survey reported talking with other veterans "as a top resource for coping with stress".¹⁵³ Finally, researchers have provided moral injury treatment in weekly group meetings.^{65,99}

Table 1. Measurable Benchmarks Administered during Study 2 and 3

Area of Interest	Description of Outcome to be Evaluated	Measure and/or Expected Outcome
Acceptability	Participant Satisfaction	Client Satisfaction Questionnaire (CSQ-8) ¹⁵⁴ satisfaction of $\geq 80\%$
	Intention to continue to use skills	Questionnaire developed for this study
	Training appropriateness	Questionnaire developed for this study
Demand	Completed sessions	$\sim 52\%$ of those who meet eligibility criteria will attend 4 to 6 sessions based on previous studies ^{97,107,110}

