	Homework Practice	Gradual increase in minutes of home practice relative to the number of minutes assigned over the 6 weeks $\sim 40\%$ of those who attend 4 to 6 sessions will complete 80% or more homework
Implementation/ Practicality	Screening/eligibility for study/ dropout	Record number of call attempts for each participant and reasons for ineligibility/decision not to participate/dropout
	Recruitment	Recruit, phone screen, and explain study to eligible participants for Study 1 within 2 weeks, Study 2 within 1 month, and Study 3 within 2 months. Obtained signed informed consent from participant.
	Retention	Among those randomized, 34/42 (81%) will attend 1 or more sessions ^{97,107,110}
	Assessment completion	For assessments attempted, 90% completion rate

Aim 3. To Evaluate the Preliminary Feasibility of the Interventions (Study 3)

In Study 3, we propose to test the refined interventions with a larger group of combat wounded veterans (N = 60 combat wounded veterans; 30 MMMI; 30 ES group). After completing the baseline measures, participants will be randomly assigned to program. We will collect information on acceptability, adherence, and implementation/practicality in the two intervention arms, as well as primary moral injury symptoms (e.g., guilt, shame), possible mechanisms of changes (e.g., acceptance, nonjudgment, compassion), and possible

secondary outcomes (e.g., mental health symptoms, substance use), which will help inform key variables to include in a large-scale sufficiently powered RCT. See Table 3.

Sample Size Determination

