Prior to determining the sample size for Study 3, we examined the literature on determination of sample size for feasibility studies.¹⁵⁴⁻¹⁵⁶ We specifically examined prior eligibility, refusal, randomization and session and data completion rates. We also considered practical aspects such as eligibility criteria, refusal and dropout rates, expected interview and data completion rates, therapist hours and length of training, supervision, fidelity coding, and timeline. Overall, the majority of feasibility studies had modest sample sizes with varying rates of participation completion: 57% (n = 21),¹⁰⁷ 81% (n = 33),⁹⁷ and 77% (n = 37).¹¹⁰ Based on averages from previous studies,^{97,107,110} we will recruit 60 combat wounded veterans. Furthermore, we expect an ineligible rate/refusal rate of 30% (n = 18) and that an additional 18.8% (n = 8) will attend no sessions and/or not complete the post-training semi-structured interview or other survey measures, for a conservative completion rate of 34 participants. Given that the MMMI and ES support group will be equal in delivery, facilitation, group size, length, home practice burden, we do not anticipate different group completion rates.

Aim 2 and 3: Examining the Intervention's Fidelity, Feasibility and Acceptability

Maintenance and Evaluation of Treatment Fidelity. We will provide ongoing assessment of treatment fidelity among facilitators following recommendations made by Borrelli¹⁷⁴. Specifically, facilitators will utilize a treatment manual that will detail session-specific components and proscribed topics, along with a checklist to ensure completion. Contact minutes per group will be recorded to ensure duration consistency across groups. Deviations from protocol will be recorded by the facilitators. Further, all sessions will be audio-recorded via state-of-the-art Intelligent Video Solutions equipment (see Equipment). [name] or [name] will listen to at least one session per cohort group to ensure adherence to the manual across time and sessions. If either facilitator falls below a predetermined performance criterion or self-reported checklist indices, two sessions per group for that facilitator will be observed until adherence meets established criteria. Facilitators will be provided feedback during weekly supervision.

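### Study 3 is stated as 30 MMMI and 30 ES, but the plan's own participant flow randomises 42, about 21 per arm

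*Combined protocol and SAP*

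**What the plan says.** Aim 3 (Study 3) appears twice, and both times gives 60 veterans split equally: "N = 60 combat wounded veterans; 30 MMMI; 30 ES group". Assignment comes late in the sequence: "After completing the baseline measures, participants will be randomly assigned to program".

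The section Sample Size Determination, also given twice, describes a flow. The starting point is "we will recruit 60 combat wounded veterans". Then "we expect an ineligible rate/refusal rate of 30% (n = 18) and that an additional 18.8% (n = 8) will attend no sessions" or will not provide post-training data, "for a conservative completion rate of 34 participants".

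Table 1, Retention row, names the denominator: "Among those randomized, 34/42 (81%) will attend 1 or more sessions". Table 1, Recruitment row, allows two months to recruit, screen and inform eligible participants for Study 3, but gives no count.

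On attendance at 4 to 6 sessions, Table 1 (Demand, completed sessions) expects about 52% "of those who meet eligibility criteria will attend 4 to 6 sessions based on previous studies". The section Evaluation of Feasibility and Acceptability expects 81% of those who qualify and agree to take part to attend 4 to 6 sessions and also complete post-training measures.

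**The concern.** Veterans who are ineligible or refuse are never assigned to an arm. If 60 are recruited and 18 are lost in this way, 60 cannot then be randomised as 30 and 30. A reader who takes the arm sizes from Aim 3 expects 43% more randomised veterans than the flow provides (60/42 = 1.43).

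This matters because participant flow is itself an outcome of a feasibility study. The plan will assess enrolment, the ability to randomise, and retention by arm. The two-month recruitment benchmark has no number of its own, so it depends on the Study 3 count. If 42 eligible veterans are recruited in two months, the benchmark is met under the flow and missed by 30% under the 30/30 statement.

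The second problem concerns the meaning of 34 or 81%. It stands for three things:

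- attending and completing measures (Sample Size Determination);
- attending at least one session (Table 1, Retention);
- attending 4 to 6 sessions and completing measures (Evaluation of Feasibility and Acceptability).

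The third does not fit the 52% in the Demand row, so the same attendance result could be judged above or below expectation.

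**Working it through.** **Inputs.** From Sample Size Determination: 60 recruited, 30% (18) ineligible or refusing, a further 18.8% (8) lost, 34 completing. From Table 1: 34/42 (81%) among those randomised, and about 52% of those eligible attending 4 to 6 sessions. From Aim 3: 30 per arm. From Evaluation of Feasibility and Acceptability: 81% attending 4 to 6 sessions.

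**The plan's flow reproduces.**

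- 60 × 0.30 = 18, and 60 − 18 = 42.
- 42 × 0.188 = 7.9, stated as 8.
- 42 − 8 = 34, and 34/42 = 0.810, stated as 81%.

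The base of the second loss is therefore 42. On 60 it would be 60 × 0.188 = 11.3, not 8. (8/42 is 19.0% rather than 18.8%, which is only rounding.)

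**The arm sizes do not reproduce.** With 1:1 allocation, 42/2 = 21 per arm, against 30 stated: 9 fewer per arm, or 30%. With equal losses, 34/2 = 17 per arm retained.

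**Precision, for illustration only.** The plan will compare retention between arms but specifies no test or interval. For two proportions of 0.81, the 95% half-width is 1.96 × √(2 × 0.81 × 0.19 / n).

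- n = 30: 1.96 × √(0.3078/30) = 0.199, about 20 points.
- n = 21: 1.96 × √(0.3078/21) = 0.237, about 24 points.

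This is a normal approximation with about 4 expected losses per arm (21 × 0.19 = 4.0), and it ignores clustering by group, so it shows scale only.

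**The 4-to-6-session expectation.** The 18 lost may be ineligible or may be refusals, in unknown proportion. Given 60 recruited, the number eligible lies between 42 (all 18 ineligible) and 60 (all 18 refusals).

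- 52% of those eligible: 0.52 × 42 = 21.8, up to 0.52 × 60 = 31.2; that is 22 to 31 veterans.
- 81% of those who qualify and agree: 0.81 × 42 = 34.0.
- Gap: 34.0 − 31.2 = 2.8, up to 34.0 − 21.8 = 12.2.
- Base needed for 52% to give 34: 34/0.52 = 65.4, more than the 60 recruited.

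The different denominators therefore narrow the conflict but do not remove it.

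**The case against.** The strongest reply is that 60, 18, 42, 8 and 34 all agree, and only the 30/30 split is out of line. It can be read as a loose 1:1 division of the recruitment target, with the losses disclosed in the next section. No stated calculation uses 30 per arm. The sample size was set from completion rates in earlier studies and from practical limits, and the 81% retention rate can be applied to whatever number is randomised. Most of this stands, and it limits the severity. It does not rescue the wording: no sentence marks 30/30 as a figure before screening, assignment follows baseline, and Table 1 gives 42 as those randomised.

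Three stronger readings are tempting and are not supported.

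- A reader might infer that the study loses power. The documents give no power, alpha or test for Study 3, so no such figure changes.
- A reader might infer that 60 were meant to be randomised and that recruitment is too small. That would need 60/0.70 = 85.7, about 86 recruited, and would contradict 60 recruited, 18, 42, 8 and 34.
- A reader might treat the gap of about 3 to 12 veterans attending 4 to 6 sessions as unconditional. It holds only if 60 is the number recruited, and its lower end is small against a benchmark that the plan marks as approximate.

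It is also fair to say that the 81% and 52% issue is separate from the arm sizes and should not raise their severity.

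**Conclusion.** The contradiction holds. As written, Study 3 states arms of 30 and 30, while its own flow delivers 42 randomised: about 21 per arm, with about 17 per arm retained. This assumes 1:1 allocation, which the stated equal arms imply, and equal losses, which agrees with the plan's expectation of no difference in completion between groups. The best-supported reading is 60 recruited, 42 randomised and 34 retained.

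The conflict in the 81% figure also holds as a separate, smaller point: three outcomes share one number, and the version for 4 to 6 sessions cannot be matched to the 52% with any eligible base up to 60.

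The severity is moderate. The statement of sample size needs correcting, and the recruitment benchmark needs a count. The loss of precision is modest (about 24 against 20 points, illustrative), and no planned analysis is invalidated.

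**What to change.** 1. In both statements of Aim 3, label 60 as the number recruited, and replace the 30/30 split with about 21 per arm randomised and about 17 per arm retained. Use the same recruited, randomised and retained figures in both copies of Sample Size Determination and in Table 1.
2. In Table 1, Recruitment row, state which count must be reached within two months.
3. Tie 81% to one outcome and one denominator. The Retention row already has both: those randomised, attending at least one session. Give completion of post-training measures its own rate in Sample Size Determination.
4. Reconcile the expectation for 4 to 6 sessions between the Demand row and Evaluation of Feasibility and Acceptability, and state the base of each percentage.

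If the sponsor did intend to randomise 60, it must say so and correct the flow. At the plan's own rates, 18, 42, 8 and 34 become about 26 (86 − 60), 60, 11 (60 × 0.188 = 11.3) and 49 (60 − 11), with about 86 recruited.

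Cost: under the best-supported reading, wording only and no extra participants, but the stated arm size becomes less favourable. Under the other reading, about 26 more veterans would have to be recruited.

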Evaluation of Feasibility and Acceptability. To evaluate feasibility and acceptability, we will rely on benchmarks proposed in the extant pilot/feasibility study literature.¹⁷⁶⁻¹⁷⁸ Specifically, we will assess methodological- (screening, recruitment, randomization, retention) and intervention- (treatment adherence) related components of the proposed protocol. Throughout recruitment and administration, we will assess for: (1) the number of veterans screened per week, (2) the number of veterans enrolled per week, (3) the proportion of screened participants who take part in the sessions, (4) the ability to randomize enrolled veterans, (5) the number of battery assessments completed, and (6) the proportion of questionnaires completed. Low rates could indicate a high level of perceived burden, limiting the feasibility of this intervention.

Specific to treatment components, we will: (1) assess the number of sessions completed by participants in each group, (2) assess the percent of completed mindfulness home practice assignments among intervention participants as compared to the home assignments from the ES group, and (3) compare the retention rate of participants assigned to the MMMI group to that of participants assigned to the ES control condition. High retention and homework completion rates will indicate that participants found the intervention acceptable and that, similar to the MMCP program (Brintz et al., in press), six sessions are acceptable. Based on prior studies conducted we anticipate 81% of those who meet study criteria and agree to participate will attend 4 to 6 sessions and complete the post-training semi-structured interview or other survey measures. Forty (40%) of those who attend 4 to 6 sessions will complete 80% or more homework, ~40% who attend 4 to 6 sessions will complete 40% to 80% of homework, and ~20% who attend 4 to 6 sessions will complete less than 40% of the homework. Acceptability will also be evaluated with the Client Satisfaction Questionnaire ($\geq 80\%$) and via two questionnaires developed for this study: (1) whether individuals intend to continue using the skills learned in the future, and (2) appropriateness of the intervention to treat moral injury.

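### The same 81% is the expected share for three different events, ranging from attending one session to attending four or more and giving post-training data

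*Combined protocol and SAP*

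**What the plan says.** Four places give an expected attendance or completion figure.

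- **Table 1, Retention row:** "Among those randomized, 34/42 (81%) will attend 1 or more sessions".
- **Sample Size Determination (the section appears twice with the same figures):** of 60 recruited, 30% (18) are expected to be ineligible or to refuse. A further 18.8% (8) "will attend no sessions and/or not complete the post-training semi-structured interview or other survey measures", "for a conservative completion rate of 34 participants". No minimum number of sessions is set beyond not attending none.
- **Evaluation of Feasibility and Acceptability:** prior studies are cited for the expectation that "81% of those who meet study criteria and agree to participate will attend 4 to 6 sessions and complete the post-training semi-structured interview" or other surveys.
- **Table 1, Demand row:** about 52% of those meeting the eligibility criteria are expected to attend four to six sessions. This row cites the same three studies as the Retention row.

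**The concern.** One percentage is attached to three events of increasing strictness: at least one session; at least one session with post-training data; and four to six sessions with post-training data. Some people normally drop out between the first session and the fourth, or finish the sessions without giving follow-up data, so the three rates would be expected to differ.

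The figures matter because feasibility is the purpose of the study and Table 1 presents them as measurable benchmarks. The plan also says that high retention will be taken to show acceptability, and it will compare retention between arms. A reader of the results could not tell whether the 81% to be matched means one session, or four or more with post-training data. The same data could be reported as meeting the expectation or missing it. The homework percentages are conditional on attending four to six sessions, so their expected base is unclear too.

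**Working it through.** **Inputs.** 60 recruited, 18 ineligible or refusing, 8 further losses, 34 completers (Sample Size Determination); 34/42 for one or more sessions (Table 1, Retention); about 52% of eligibles for four to six sessions (Table 1, Demand); 81% for four to six sessions plus post-training data (Evaluation of Feasibility and Acceptability).

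**1. The plan's own figure reproduces.** 60 × 0.30 = 18; 60 − 18 = 42; 42 − 8 = 34; 34/42 = 81.0%. Using the stated rate, 42 × (1 − 0.188) = 34.1. (8/42 is 19.0% rather than 18.8%; this is rounding and does not move the 34.)

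**2. What 81% means on 42 people.** 33/42 = 78.6%, 34/42 = 81.0%, 35/42 = 83.3%. Only 34 people rounds to 81%.

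**3. The three events compared.** In this flow the people randomised and the people who are eligible and agree are the same 42. Let A be one or more sessions, B be A plus post-training data, and C be four to six sessions plus post-training data. Everyone in C is in B, and everyone in B is in A. If each contains 34 people, they are the same 34. So nobody attends only one to three sessions, and every attender gives post-training data. If some people agreed but were never randomised, the base for C would exceed 42 and the clash would be larger.

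**4. One result, two descriptions (each expectation read as a minimum).** Suppose 34 attend at least once and 33 of them attend four to six sessions.
- Retention row: 34/42 = 81.0%, met.
- Demand row: 33/60 = 55.0%, 33/51 = 64.7% or 33/42 = 78.6%, depending on how many of the 18 were eligible; met in each case.
- Narrative expectation: at most 33/42 = 78.6%, missed even if all 33 give post-training data.

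**5. The Demand row on the base of 42.** The plan does not split the 18 losses into ineligible and refusing, so the split is an assumption and the whole range is shown.

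| Assumed split of the 18 | Eligible | 52% of eligible | Share of 42 | Short of 34 by |
|---|---|---|---|---|
| All refused | 60 | 31.2 | 74.3% | 2.8 |
| 9 refused, 9 ineligible | 51 | 26.5 | 63.1% | 7.5 |
| All ineligible | 42 | 21.8 | 52.0% | 12.2 |

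Within the 60-to-42-to-34 flow, Table 1 therefore leaves about 3 to 12 of its 34 attenders at one to three sessions. The narrative section leaves none.

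**6. If 60 is the number randomised.** The Study 3 description ("N = 60 combat wounded veterans; 30 MMMI; 30 ES group") can be read this way. Then 0.81 × 60 = 48.6; 48.6/0.52 = 93.5 eligible; 60/93.5 = 64.2%. The 52% and 81% figures then agree if about 64% of eligibles take part, a rate the plan does not give. The mismatch in step 3 remains, because it does not depend on the size of the base.

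**7. Effect on the homework base.** 40% of 34 is 13.6 people; 40% of 21.8 to 31.2 is 8.7 to 12.5.

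**The case against.** The best defence is that these are forecasts, not thresholds. The narrative figure is something the investigators anticipate, and the 52% is marked as approximate. Sessions attended will be recorded by group whatever was forecast. The example in step 4 turns on one participant, 1/42 = 2.4 points, while the standard error of 81% on 42 people is √(0.81 × 0.19/42), about 6 points. All of that stands. It limits the consequence but does not make the three definitions agree.

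A reader might infer that 52% and 81% contradict each other outright, by 29 points. The documents do not support that. The 52% is of those eligible, while the 81% is of those eligible and agreeing, and a lower rate on a wider base is to be expected. The 29-point gap needs all 18 losses to be ineligible. At the other limit the gap is about 3 people around an approximate figure, and it vanishes under the reading in step 6.

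A reader might also infer that the retention figure was copied into the narrative by mistake. 100% − 18.8% = 81.2% and the similar wording about post-training data make that plausible. But the narrative credits prior studies, and one of the three cited had 81% completion (the other two had 57% and 77%). The origin is not established, and the point does not need it.

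Two further cautions are fair. The narrative accepts an interview or other surveys, so only some post-training data is required of each attender. And the 60-to-42-to-34 flow belongs to Study 3, whereas Table 1 and the narrative also cover Study 2.

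**Conclusion.** The inconsistency is real and lies between the Retention row, Sample Size Determination and the narrative section. On the Study 3 base of 42, all three place 34 people (81%) in events that coincide only if no one attends just one to three sessions and every attender gives post-training data. The plan does not state this. The conclusion assumes that those randomised and those eligible and agreeing are the same people, as in the plan's own flow.

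The Demand row supports the point but does not prove it. On 42 it implies about 22 to 31 people at four to six sessions against 34, depending on an unstated split, and it can be reconciled with 81% if 60 are randomised and about 64% of eligibles agree.

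It would be wrong to infer that the design is compromised. No go/no-go rule, sample size or power figure rests on these percentages, and the arithmetic behind 34/42 is sound. The consequence is that feasibility results could be judged against an ambiguous benchmark. That is worth correcting, and it is easy to correct.

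**What to change.** Before data are seen, reconcile Sample Size Determination, the Demand and Retention rows of Table 1, and Evaluation of Feasibility and Acceptability. State which event the 81% describes. Give each of these its own labelled denominator and expected percentage: one or more sessions; four to six sessions; post-training measures completed; and any combined definition of a completer.

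- **If 81% is the figure for one or more sessions:** keep the Retention row as it is. Replace the 81% in the narrative with a four-to-six-session figure consistent with the Demand row on a stated denominator. Report the completer definition in Sample Size Determination separately, so that attendance and assessment completion are not merged.
- **If 81% is meant for four to six sessions:** revise the Retention row, and check the Demand row against it.

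The cost is some rewording and restating one or two benchmark figures. One stated expectation may become less favourable. Design, sample size and data collection do not change.
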